12.3. Appendix 3: Assessment Windows

12.3.1. Definitions of Assessment Windows for Analyses

Use nominal time of assessment.

12.4. Appendix 4: Study Phases and Treatment Emergent Adverse Events

12.4.1. Study Phases

Assessments and events will be classified according to the time of occurrence relative to treatment start date.

Study Phase	Definition
Pre-Treatment	Date ≤ Study Treatment Start Date
On-Treatment	Study Treatment Start Date < Date ≤ Study Treatment Stop Date +1
Post-Treatment	Date > Study Treatment Stop Date +1

12.4.1.1. Study Phases for Concomitant Medication

Study Phase	Definition
Prior	If medication end date is not missing and is before date of start of treatment
Concomitant	Any medication that is not a prior

NOTES:

- Please refer to [Appendix 7: Reporting Standards for Missing Data](#) for handling of missing and partial dates for concomitant medication. Use the rules in this table if concomitant medication date is completely missing.

12.4.2. Treatment Emergent Flag for Adverse Events

Flag	Definition
Treatment Emergent	
 • If AE onset date is on or after treatment start date & on or before treatment stop date. • Study Treatment Start Date ≤ AE Start Date ≤ Study Treatment Stop Date +1

NOTES:

- If the study treatment stop date is missing, then the AE will be considered to be On-Treatment.
- Time of study treatment dosing and start/stop time of AEs should be considered, if collected.

12.5. Appendix 5: Data Display Standards & Handling Conventions

12.5.1. Reporting Process

Software	

 The currently supported versions of SAS Studio 3.6 (Basic Edition) will be used. 	
Reporting Area	
HARP Server	: \\UK1SALX00175.CORPNET2.com
HARP Compound	: \arprod\gsk1325756
Analysis Datasets	

 Analysis datasets will be created according to Legacy GSK A&R dataset standards. 	
Generation of RTF Files	

 RTF files will be generated for final analysis outputs 	

12.5.2. Reporting Standards

General	

 The current GSK Integrated Data Standards Library (IDSL) will be applied for reporting, unless otherwise stated (IDSL Standards Location: https://spope.gsk.com/sites/IDSLLibrary/SitePages/Home.aspx): 
 4.03 to 4.23: General Principles 5.01 to 5.08: Principles Related to Data Listings 6.01 to 6.11: Principles Related to Summary Tables 7.01 to 7.13: Principles Related to Graphics Do not include subject level listings or figures in the main body of the GSK Clinical Study Report. All subject level listings should be located in the modular appendices as ICH or non-ICH listings 	
Formats	

 GSK IDSL Statistical Principles (5.03 & 6.06.3) for decimal places (DP's) will be adopted for reporting of data based on the raw data collected, unless otherwise stated. Numeric data will be reported at the precision collected on the eCRF or provided by vendor. The reported precision from non eCRF sources will follow the IDSL statistical principles but may be adjusted to a clinically interpretable number of DP's. 
 For NETs the individual data will be provided according to the appropriate level of precision for the listings. 	
Planned and Actual Time	

 Reporting for tables, figures and formal statistical analyses: 
 Planned time relative to dosing will be used in figures, summaries, statistical analyses and calculation of any derived parameters, unless otherwise stated. The impact of any major deviation from the planned assessment times and/or scheduled visit days on the analyses and interpretation of the results will be assessed as appropriate. Reporting for Data Listings: 
 Planned and actual time relative to study drug dosing will be shown in listings (Refer to IDSL Statistical Principle 5.05.1). Unscheduled or unplanned readings will be presented within the participant's listings. 	

Unscheduled Visits	

 Unscheduled visits will not be included in summary tables and/or figures. All unscheduled visits will be included in listings. 	
Descriptive Summary Statistics	
Continuous Data	Refer to IDSL Statistical Principle 6.06.1
Categorical Data	N, n, frequency, %
Graphical Displays	

 Refer to IDSL Statistical Principals 7.01 to 7.13. 	

12.5.3. Reporting Standards for Pharmacokinetic

Pharmacokinetic Concentration Data	
PC Windows Non-Linear (WNL) File	PC WNL file (CSV format) for the non compartmental analysis by Clinical Pharmacology Modelling and Simulation function will be created according to GUI_51487 and PKONE document. Note: Concentration values will be imputed as per GUI_51487
Descriptive Summary Statistics, Graphical Displays and Listings	Refer to IDSL PK Display Standards. Refer to IDSL Statistical Principle 6.06.1. Note: Concentration values will be imputed as per GUI_51487 for descriptive summary statistics/analysis and summarized graphical displays only. Additionally , include geometric mean and 90% CI for the summary of blood concentration data
NONMEM/Pop PK File	Pop-PK file (CSV format) for the POP-PK analysis by Clinical Pharmacology Modelling and Simulation function will be created according to the data specification detailed in Appendix 9 .
NONMEM/PK/PD File	Not applicable.
Pharmacokinetic Parameter Derivation	
PK Parameter to be Derived by Programmer	None.
Pharmacokinetic Parameter Data	
Is NQ impacted PK Parameters Rule Being Followed	No.
Descriptive Summary Statistics, Graphical Displays and Listings	Refer to IDSL PK Display Standards.

12.6. Appendix 6: Derived and Transformed Data

12.6.1. General

Multiple Measurements at One Analysis Time Point

 • Mean of the measurements will be calculated and used in any derivation of summary statistics but if listed, all data will be presented. • If there are two values within a time window (as per Section 12.3.1) the value closest to the target day for that window will be used. If values are the same distance from the target, then the mean will be taken. 
 ○ For NETs: If there are unscheduled visits between screening and visit 2 use the last unscheduled visit prior to visit 2. • Participants having both High and Low values for Normal Ranges at any post-baseline visit for safety parameters will be counted in both the High and Low categories of “Any visit post-baseline” row of related summary tables. This will also be applicable to relevant Potential Clinical Importance summary tables.
Study Day

 • Calculated as the number of days from First Dose Date: 
 • Ref Date = Missing → Study Day = Missing • Ref Date < First Dose Date → Study Day = Ref Date – First Dose Date • Ref Date ≥ First Dose Date → Study Day = Ref Date – (First Dose Date) + 1

12.6.2. Study Population

Treatment Compliance

 • Treatment compliance will be calculated based on the formula: $\text{Treatment Compliance} = \text{Number of Actual Doses} / (\text{Planned Treatment Duration in Days} * \text{Frequency})$ • Frequency is 2 for BID Treatment compliance could be greater than 100% if there are events of overdose. • Planned Treatment Duration is defined as 14 days
Extent of Exposure

 • Number of days of exposure to study drug will be calculated based on the formula: $\text{Duration of Exposure in Days} = \text{Treatment Stop Date} - (\text{Treatment Start Date}) + 1$
Age

 • Age will be calculated based off the date participants signed consent forms • GSK standard IDSL algorithms will be used for calculating age where birth date will be imputed as follows: 
 ○ Any participant with a missing day will have this imputed as day ‘15’. ○ Any participant with a missing date and month will have this imputed as ‘30th June’. • Birth date will be presented in listings as ‘YYYY’.
Smoking Status

 • If the last smoked date (SUSMLSDT) is missing and a partial date (SUSMLSD) is not missing, then the following imputation should be applied to the partial smoking date for use in the reclassification of smoking status calculation: 
 ○ ‘01’ will be used for the day and ‘Jan’ will be used for the month.

Treatment Compliance

 Former smokers will be reclassified as current smokers if screening date – last smoked date < 183 days.

12.6.3. Efficacy

Change from Baseline

 Change from Baseline will be calculated based on the formula: Change from Baseline = Value – Value on day 1 
 Use the most recent pre-dose value for baseline. In the case where there is a bad sample on day 1 use screening

12.6.4. Dataset to Protocol Mapping

Protocol Variable	BICAT (BIOMARK)	MITEST (MICROSCOPY)	MITSTD (MICROSCOPY)	SPECTYPE (MICROSCOPY)
Reduction in sputum NET area quantification by microscopy		AK005	26	C13278
Reduction in sputum NETs (quantified by Histone-elastase complexes)	HISTELAS			C13278
Reduction in sputum NETS (quantified by Deoxyribonucleic acid [DNA]-elastase complexes)	DNAELAS			C13278
Change from baseline in sputum resistin levels	RESIST			C13278
Change from baseline in the ratio of sputum NETs to sputum neutrophils		AW002		C13278
Change from baseline in sputum elastase activity	ELASTASE			C13278

Protocol Variable	BICAT (BIOMARK)	MITEST (MICROSCOPY)	MITSTD (MICROSCOPY)	SPECTYPE (MICROSCOPY)
Change from baseline in peripheral blood neutrophil NET formation (DNA release, microscopy)		AK005	8	C12434

12.7. Appendix 7: Reporting Standards for Missing Data

12.7.1. Premature Withdrawals

Element	Reporting Detail
General	
 Participant study completion (i.e. as specified in the protocol) was defined as those who have completed the assessments supporting the primary endpoint Withdrawn participants may be replaced in the study. All available data from participants who were withdrawn from the study will be listed and all available planned data will be included in summary tables and figures, unless otherwise specified.

12.7.2. Handling of Missing Data

Element	Reporting Detail
General	
 Missing data occurs when any requested data is not provided, leading to blank fields on the collection instrument: 
 These data will be indicated by the use of a "blank" in participant listing displays. Unless all data for a specific visit are missing in which case the data is excluded from the table. Answers such as "Not applicable" and "Not evaluable" are not considered to be missing data and should be displayed as such.
Outliers	
 Any participants excluded from the summaries and/or statistical analyses will be documented along with the reason for exclusion in the clinical study report.

12.7.2.1. Handling of Missing and Partial Dates

Element	Reporting Detail
General	
 Partial dates will be displayed as captured in participant listing displays.
Adverse Events	
 The eCRF allows for the possibility of partial dates (i.e., only month and year) to be recorded for AE start and end dates; that is, the day of the month may be missing. In such a case, the following conventions will be applied for calculating the time to onset and the duration of the event: 
 Missing Start Day: First of the month will be used unless this is before the start date of study treatment; in this case the study treatment start date will be used and hence the event is considered On-treatment as per Appendix 4: Study Phases and Treatment Emergent Adverse Events. Missing Stop Day: Last day of the month will be used, unless this is after the stop date of study treatment; in this case the study treatment stop date will be used. Completely missing start or end dates will remain missing, with no imputation applied. Consequently, time to onset and duration of such events will be missing. If treatment phase for an AE is missing due to missing dates class as on-treatment
Concomitant Medications/ Medical History	
 Partial dates for any concomitant medications recorded in the CRF will be imputed using the following convention: 
 If the partial date is a start date, a '01' will be used for the day and 'Jan' will be used for the month If the partial date is a stop date, a '28/29/30/31' will be used for the day (dependent on the month and year) and 'Dec' will be used for the month. The recorded partial date will be displayed in listings.

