#### **Treatment Groups and Duration:**

The study will consist of a screening/baseline period of up to 30 days, a 2 week treatment period, and a 1-week follow-up visit. The study duration, including screening and follow-up, is not expected to exceed 2 months for participants in the study.

Study treatment will consist of two groups: danirixin 35mg HBr orally twice daily or matching placebo.

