# 9.2.1. Time Period and Frequency for Collecting AE and SAE Information

- All SAEs will be collected from the signing of the ICF until the follow-up visit at the time points specified in the SoA (Section 2).
- All AEs will be collected from the signing of the ICF until the follow-up visit at the time points specified in the SoA (Section 2).
- Medical occurrences that begin before the start of study treatment but after obtaining informed consent will be recorded on the Medical History/Current Medical Conditions section of the CRF not the AE section.
- All SAEs will be recorded and reported to the sponsor or designee immediately and under no circumstances should this exceed 24 hours, as indicated in Appendix 4. The investigator will submit any updated SAE data to the sponsor within 24 hours of it being available.

- Investigators are not obligated to actively seek AEs or SAEs in former study participants. However, if the investigator learns of any SAE, including a death, at any time after a participant has been discharged from the study, and he/she considers the event to be reasonably related to the study treatment or study participation, the investigator must promptly notify the sponsor.
- The method of recording, evaluating, and assessing causality of AEs and SAEs and the procedures for completing and transmitting SAE reports are provided in Appendix 4

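### The missing-start-day rule for adverse events does not check the month, so an event recorded in a month wholly before treatment is re-dated to the first dose and labelled On-treatment

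*SAP*

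**What the plan says.** SAP 12.7.2.1 covers AEs whose start or end date is partial, "that is, the day of the month may be missing". It offers its conventions as a way to compute onset time and event duration. For a missing start day the rule reads "First of the month will be used unless this is before the start date of study treatment". Where that first day does precede dosing, the SAP draws the consequence itself: "in this case the study treatment start date will be used and hence the event is considered On-treatment as per Appendix 4". For a missing stop day, the last day of the month is used, capped at the treatment stop date. Nothing requires the imputed stop to fall on or after the imputed start.

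SAP 12.4.2 sets the treatment-emergent flag by "Study Treatment Start Date ≤ AE Start Date ≤ Study Treatment Stop Date +1", so an onset on the treatment start date is treatment emergent. SAP 12.4.1 defines the Pre-Treatment phase by "Date ≤ Study Treatment Start Date", so the same date is Pre-Treatment there.

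The Protocol synopsis allows "a screening/baseline period of up to 30 days". Protocol 9.2.1 states "All SAEs will be collected from the signing of the ICF until the follow-up visit" and says the same of all AEs. The same section then directs occurrences that begin after consent but before treatment to the medical-history part of the CRF instead of the AE part.

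**The concern.** When the recorded month is the month treatment began, the order of onset and first dose is unknown, and moving the onset to the first dose is a defensible cautious convention. When the recorded month is earlier, the order is known: the event began before dosing. The first of an earlier month always precedes treatment start, so the substitution always applies there, and it replaces a known fact with a false one.

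What is at stake is the study phase, the treatment-emergent flag, the time to onset and the duration of such a record. The last two are what the conventions exist to calculate.

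**Working it through.** The plan gives no figure to reproduce. The check applies the written rules to dates and then counts how often the recorded month settles the question.

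**Inputs.** Start-day and stop-day rules: SAP 12.7.2.1. Phase: SAP 12.4.1. Flag: SAP 12.4.2. Treatment of 14 days: SAP 12.6.2. Screening of up to 30 days: Protocol synopsis. The dates below are illustrative. The SAP gives no AE duration formula, so stop - start + 1 is assumed, as SAP 12.6.2 uses for exposure.

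**Worked example.** Treatment starts 20 July 2018 and stops 2 August 2018.

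| Recorded onset | Imputed onset, SAP rule | Flag under 12.4.2 | Imputed onset with month check | Flag |
|---|---|---|---|---|
| June 2018 | 20 July | emergent | 1 June | not emergent |
| July 2018 | 20 July | emergent | 20 July | emergent |
| August 2018 | 1 August | emergent | 1 August | emergent |

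Only the June row differs, and June lies wholly before the first dose.

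- *Time to onset.* By the study-day formula in SAP 12.6.1, the SAP rule puts the June event on Day 1 (20 July - 20 July + 1). With the month check it is Day -49 (1 June - 20 July).
- *Duration.* If the stop is also recorded as June 2018, the stop-day rule gives 30 June. Duration is 30 June - 20 July + 1 = -20 + 1 = -19 days.
- *Phase.* An imputed date of 20 July meets the Pre-Treatment condition in 12.4.1, because that condition includes equality. It is nevertheless treatment emergent under 12.4.2 and On-treatment by the words of 12.7.2.1. The three sections do not agree about the first dosing day.

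**How often the earlier month arises.** Assume the record is pre-dose, is on the AE page and lacks its day, and that onsets are spread evenly over s days of screening and start dates evenly over the calendar. An onset t days before treatment falls in an earlier month with probability about t/30.44, where 30.44 is the mean month length in days. Averaging over t = 1 to s gives ((s + 1)/2)/30.44:

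- s = 7: 4/30.44 = 0.131
- s = 14: 7.5/30.44 = 0.246
- s = 30: 15.5/30.44 = 0.509

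Direct enumeration of every start date in 2017 and 2018 gives 13.2%, 24.7% and 50.9%. Under the SAP rule, 100% of these pre-dose onsets are flagged treatment emergent. With the month check the figures are 86.8%, 75.3% and 49.1%. What remains are same-month onsets, whose order is truly unknown. Earlier-month onsets flagged as emergent fall from 100% to 0%.

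**The case against.** The strongest reply is that the problem is largely handled upstream. Protocol 9.2.1 sends post-consent, pre-dose occurrences to Medical History, and the SAP gives concomitant medication and medical history their own date rule. An event known by its month to be pre-dose should seldom reach the AE page at all. That stands as a limit on the number of records. It does not make the rule right: the same protocol section collects AEs and SAEs from consent, and the SAP defines a Pre-Treatment phase for events, so such records remain possible. The SAP's listing of AEs for subjects outside the mITT population adds nothing here, because those subjects have no treatment start date.

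Three stronger readings are tempting, and the documents do not support them.

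- *Pre-dose events are counted against danirixin.* The rule applies alike to both arms. The titles of AE Tables 3.1 to 3.4 and 3.7 do not restrict them to treatment-emergent events. If they are unfiltered, moving an onset changes no count.
- *The 3:1 allocation tilts the comparison.* More moved events would fall in the larger arm only because more participants are in it. Pre-dose onsets cannot depend on randomized treatment, so no difference in rate is expected.
- *Up to half of AEs are misclassified.* The 13%, 25% and 51% apply only to pre-dose AE-page records with a missing day. They are calendar arithmetic and do not measure impact.

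It is also fair to say that partial dates appear in listings as captured, so a reader of the AE listing would see the true month. Appendix 11 plans no summary table of onset time or duration, and the safety analysis is descriptive.

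**Conclusion.** The rule is wrong as written, and the point is minor. An AE with a missing start day and a recorded month before the treatment-start month is always re-dated to the first dose, called On-treatment and flagged treatment emergent. Its time to onset is wrong, and its duration is negative if it stopped before dosing. This follows from the text alone.

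The size is not known. The documents give no count of partial AE dates. With 19 completers, 14 days of treatment and the medical-history instruction, few records are likely, possibly none. The conditional shares rest on evenly spread onsets and start dates. Any effect on the AE summaries depends on a filter that the SAP does not specify. If the tables do use the flag, one moved event is 1/18 = 5.6% or 1/6 = 16.7% of an arm at the planned sizes, so a single record could be visible.

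**What to change.** In SAP 12.7.2.1, make the start-day rule depend on the recorded month and year:

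- same month and year as treatment start: use the treatment start date, as now;
- earlier month: use the first of the recorded month and classify the event as Pre-treatment;
- later month: use the first of that month, as now.

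The first of an earlier month can precede consent. In the example it is 1 June, while 30 days before 20 July is 20 June. This does not matter for phase, and the listing still shows the date as captured.

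Also reconcile 12.4.1, which puts the treatment start date in Pre-Treatment, with 12.4.2 and 12.7.2.1, which treat it as treatment emergent or On-treatment. State whether Tables 3.1 to 3.4 and 3.7 use the treatment-emergent flag. The two recording instructions in Protocol 9.2.1 should be reconciled as well.

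The month condition costs one SAP sentence and one programming condition. The other items are wording. No new data are needed, and the same-month convention is unchanged.

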12.8.2. ECG

ECG Parameter	PCI Range	Unit
Absolute QTc Interval (QTcB, QTcF)	<300 or >500	msec
QT Interval	<300 or >500	msec
PR Interval	<120 or >210	msec
QRS Interval	<70 or >125	msec
Heart Rate	<35 or >120	bpm

Values based on the mean of triplicate

12.8.3. Vital Signs

Vital Sign Parameter	PCI Range	Unit
Systolic Blood Pressure	<90 or >160	mmHg
Diastolic Blood Pressure	<40 or >110	mmHg
Heart Rate	<35 or >120	bpm
Respiration Rate	<8 or >30	breaths /min

12.9. Appendix 9: Population Pharmacokinetic (PopPK) Analyses

12.9.1. Population Pharmacokinetic (PopPK) Dataset Specification

12.9.1.1. Handling Missing Demographic and Covariate Data

Missing demographic and covariate data will not be imputed.

12.9.1.2. Handling Missing Dose Times

Missing dose time information will be handled on a case by case basis by imputing this information based on prior dosing times or based on recorded PK collection times. The details of these imputations will be described in the report.

12.9.1.3. Handling Missing Times of PK Samples

Missing times for PK will be handled on a case by case basis by imputing this information based on the dose time and/or times of other PK. The details of these imputations will be described in the report.

12.9.1.4. Handling of PK Data Below the Lower Limit of Quantification

Any PK data below the lower limit of quantification will be set to missing.

12.9.1.5. Dataset Specification

General description and rules:

- Missing or unknown values in covariates, if not to be imputed, will be assigned -99.
- The dataset is sorted by STUD, SUBJID, DATE, CTIM, EVID descending.
- The data items (columns) in the analysis-ready data file will be provided the same order as follows.
- Non-quantifiable (NQ) concentration values will be included as detailed for the CONC variable.
- Non-numerical concentration values (such as NS, NR, NA) will not be included.
- Placebo subjects will not be included.
- The dataset will be a comma delimited ASCII text file and will be named:
 - *NM.compound.study.PK.v1.csv*
 - Where “compound” is the compound name (e.g. GSK1234567) and “study” is the study number (e.g. 207551).

Variable	Label (Variable description)	Type	Units	Missing value	Codes/Derivation/Notes
ID	NONMEM subject identifier	Integer	None	Never	Sequential subject identifier across study after data is sorted by STUD, SUBJID, DATE, RTFD, EVID. Numbering to start at 1. To be entered in all rows for each subject.
STUDYID	Unique identifier for a study	Char	None	Never	207551 for all records
STUD	Study ID	Num	None	Never	207551 for all records
SUBJID	Subject identifier for study	Char	None	Never	Subject identifier, which must be unique within the study. The identification number of the subject as recorded on the CRF. Exclude placebo subjects. Include subjects who have received IP and have at least one measureable drug concentration. To be entered in all rows for each subject.
COUNTRY	Country	Char	None	Never	Country of the investigational site in which the subject participated in the trial; e.g. USA. To be entered in all rows for each subject.
SITEID	Unique identifier for a study site	Num	None	Never	e.g. PPD any lead zero should not be included. To be entered in all rows for each subject.
CONC	Drug Concentration	Num	ng/mL	Never	CONC=0 for PK_GSK1325756 records. No sample (NS), insufficient sample (IS) and no result (NR) records will be excluded from dataset. CONC='.' for PK_GSK1325756 records < LOQ (i.e. if drug conc is NQ).
LNCONC	Natural log of CONC column	Num	ng/mL	Never	Natural log of CONC column. If CONC=0, then LNCONC='.'.
LLQ	Lower Limit of quantification	Num	ng/mL	Never	LLQ=5 or from source data if different. To be entered in all rows for each

Variable	Label (Variable description)	Type	Units	Missing value	Codes/Derivation/Notes
					subject.
LNLLQ	Natural log of LLQ column	Num	ng/mL	Never	Natural log of LLQ column. If LLQ=0, then LNLLQ='.'.
MATRIX	Sample matrix	Num	None	Never	MATRIX=1 (blood).
MATRTEXT	Sample matrix text	Char	None	Never	Text corresponding to code for MATRIX. Enter 'Blood' for all rows.
LABL	Label describing the record	Char	None	Never	LABL explains the type of measurement for CONC for the current record. LABL=DOSE_GSK1325756 for dose record. LABL=PK_GSK1325756 for blood concentration record.
DATE	Date of Record	MM/DD/YYYY	None	Never	Date of record.
DATETIME	Date and time of record	MM/DD/YYYY HH:MM:SS	None	Never	Date and time of record.
DAY	Study day number of record	Num	None	Never	Day of study relative to first IP dose.
NDAY	Nominal day	Num	day	Never	Schedule visit day of study relative to first IP dose.
NOMT	Nominal time since FIRST IP dose	Num	h	Never	Nominal time of study relative to first IP dose. NOMT=0 for first dosing record only.
NOMTLD	Nominal time since LAST IP dose prior to sample	Num	h	Never	Nominal time of study relative to last IP dose prior to sample. NOMTLD=0 for dosing records.
RTFD	Relative time from FIRST IP dose to current sample time	Num	h	Never	Actual time from FIRST dose of IP.
RTLTD	Relative time from LAST IP dose prior to sample	Num	h	Never	Actual time from last dose of IP prior to sample. When LABL=DOSE_GSK1325756, RTLTD=0. For pre-dose PK sample on Day 7, RTLTD is relative to the previous dose.
DOSE	Dose amount	Num	mg	Never	DOSE=35. To be entered in all rows for each subject.

Variable	Label (Variable description)	Type	Units	Missing value	Codes/Derivation/Notes
DRUG	Name of drug	Char	None	Never	DRUG=GSK1325756. To be entered in all rows for each subject.
REG	Dosing Regimen	Integer	None	Never	REG=2 for BD. To be entered in all rows for each subject.
REGTEXT	Subject dose regimen text	Char	None	Never	REGTXT=BD, text corresponding to code for REG. To be entered in all rows for each subject.
ROUT	Route of administration	Integer	None	Never	ROUT=1 for PO. To be entered in all rows for each subject.
ROUTTEXT	Subject route of administration text	Char	None	Never	ROUTTEXT=PO, text corresponding to code for ROUT. To be entered in all rows for each subject.
CMT	NONMEM Compartment code	Integer	None	Never	CMT=1 for DOSE_GSK1325756 records. CMT=2 for PK_GSK1325756 records.
EVID	NONMEM Event ID	Integer	None	Never	EVID=1 for LABL= DOSE_GSK1325756. EVID=0 for LABL= PK_GSK1325756.
AMT	NONMEM Amount of drug administered	Num	mg	Never	AMT=0 for LABL= PK_GSK1325756 records. AMT=35 for LABL= DOSE_GSK1325756 records.
II	NONMEM Inter-dose interval	Integer	h	Never	II=0 for LABL= PK_GSK1325756. II=12 for LABL= DOSE_GSK1325756, except II=0 for LABL= DOSE_GSK1325756 on Day 1 only.
SS	Steady-state data item	Integer	None	Never	SS=0 for LABL= PK_GSK1325756 records. SS=1 for LABL= DOSE_GSK1325756 records, except SS=0 for LABL= DOSE_GSK1325756 records on Day 1 only.
RATE	NONMEM Rate of drug infusion	Integer	None	Never	RATE=0 for LABL= PK_GSK1325756 records. RATE=-2 for LABL= DOSE_GSK1325756 records.

Variable	Label (Variable description)	Type	Units	Missing value	Codes/Derivation/Notes
MDV	NONMEM Missing data value	Integer	None	Never	MDV=1 for LABL=DOSE_GSK1325756 records. MDV=0 for LABL=PK_GSK1325756 records. MDV=1 for LABL=PK_GSK1325756 records < LOQ (NQ).
VIS	Visit number	Integer	None	Never	From source data.
POP	Population	Integer	None	Never	POP=1, for COPD. To be entered in all rows for each subject.
POPTXT	Subject population text	Char	None	Never	POPTXT=COPD, text corresponding to code for POP. To be entered in all rows for each subject.
COH	Cohort	Integer	None	Never	COH=1. To be entered in all rows for each subject.
AGE	Subject Age	Integer	year	If missing impute with -99	From source data. To be entered in all rows for each subject.
SEX	Subject gender	Integer	None	Never	0=Male, 1=Female To be entered in all rows for each subject.
SEXTEXT	Subject gender text	Char	None	Never	Text corresponding to code for SEX, e.g. MALE or FEMALE). To be entered in all rows for each subject.
BMI	Baseline Body Mass Index	Num	kg/m ²	If missing impute with -99	Ensure consistent with S&P formula. E.g. Formula: Weight(kg)/(height(m)**2) To be entered in all rows for each subject.
BSA	Baseline Body Surface Area	Num	m ²	If missing impute with -99	Formula: BSA (m ²) = 0.024265 • Height(cm) ^{0.3964} • Weight(kg) ^{0.5378} Ensure consistent to with S&P formula. To be entered in all rows for each subject.
WT	Baseline Subject weight	Num	kg	If missing impute with -99	From source data. To be entered in all rows for each subject.
HT	Baseline Subject height	Num	m	If missing impute with -99	From source data. To be entered in all rows for each subject.
RACE1	Subject race code1	Integer	None	Never	From source data e.g. 1=African American / African

Variable	Label (Variable description)	Type	Units	Missing value	Codes/Derivation/Notes
					Heritage 2=American Indian or Alaska Native 3=Asian – Central / South Asian Heritage 4=Asian – East Asian Heritage 5=Asian – Japanese Heritage 6=Asian – South East Asian Heritage 7=Asian – Mixed Race 8=Native Hawaiian or other Pacific Islander 9=White – Arabic / North African Heritage 10=White – White / Caucasian / European Heritage 11=White – Mixed Race 12=Mixed Race To be entered in all rows for each subject.
RACE1TXT	Subject race text	Char	None	Never	Text corresponding to code for RACE1 To be entered in all rows for each subject.
RACE2	Subject race code2	Integer	None	Never	1=East Asian: Asian – East Asian Heritage & Asian – Japanese Heritage 2=White: White – Arabic / North African Heritage White – White / Caucasian / European Heritage 3=African: African American / African Heritage; 4=Other: American Indian or Alaska Native; Asian – Central / South Asian Heritage; Asian – South East Asian Heritage; Asian – Mixed Race; Native Hawaiian or other Pacific Islander; White – Mixed Race & Mixed Race To be entered in all rows for each subject.
RACE2TXT	Subject race text	Char	None	Never	Text corresponding to code for RACE2 To be entered in all rows for each subject.
ETHN	Subject ethnicity	Num	None	Never	From source data definition. E.g 1=Hispanic or Latino, 2=Non-

Variable	Label (Variable description)	Type	Units	Missing value	Codes/Derivation/Notes
					Hispanic To be entered in all rows for each subject.
ETHNTEXT	Subject ethnicity text	Char	None	Never	Text corresponding to code for ETHN. To be entered in all rows for each subject.
REGN	Region for subject	Num	None	Never	1 = East Asia (to include Japan, South Korea and Taiwan) 2 = Rest of the World (to include all other countries) To be entered in all rows for each subject.
SMOK	Subject smoking status	Integer	None	Never	0=Non-smoker, 1=Smoker, 2=Former smoker To be entered in all rows for each subject. Smoking status at baseline.
SMOKTEXT	Subject smoking status text	Char	None	Never	Text corresponding to code for SMOK. To be entered in all rows for each subject.
CMED1	Identifier for on-treatment COPD concomitant medication	Num	None	Never	0 = no concomitant use 1 = intermittent use 2 = continuous use To be entered in all rows for each subject.
CMED1TEXT	Subject CMED1 text	Char	None	Never	Text corresponding to code for CMED1. To be entered in all rows for each subject.
CRCL	Baseline Creatinine Clearance	Num	mL/min	If missing impute with -99	From source data. OR Specify appropriate formula e.g. Creatinine Clearance will be calculated based on the Cockcroft-Gault equation. 
 CrCL (ml/min) = $[140 - \text{AGE (in years)}] * \text{Weight(kg)} * 0.85$ (for female patients) / $[72 * \text{Serum Creatinine (micromol/L)} * 0.0113]$ Delete one as appropriate and ensure consistency with S&P

Variable	Label (Variable description)	Type	Units	Missing value	Codes/Derivation/Notes
					formula 
 To be entered in all rows for each subject.
CMED2	Identifier for on-treatment gastric acid reducing concomitant medication	Num	None	Never	0 = no concomitant use 1 = intermittent use 2 = continuous use To be entered in all rows for each subject.
CMED2TEXT	Subject concomitant medication text	Char	None	Never	Text corresponding to code for CMED2. To be entered in all rows for each subject.
CMED3	Identifier for on-treatment gastric acid increasing concomitant medication	Num	None	Never	0 = no concomitant use 1 = intermittent use 2 = continuous use To be entered in all rows for each subject.
CMED3TEXT	Subject concomitant medication text	Char	None	Never	Text corresponding to code for CMED3. To be entered in all rows for each subject.
CMED4	Identifier for on-treatment p-gp inhibitor concomitant medication	Num	None	Never	0 = no concomitant use 1 = intermittent use 2 = continuous use To be entered in all rows for each subject.
CMED4TEXT	Subject CMED4 text	Char	None	Never	Text corresponding to code for CMED4. To be entered in all rows for each subject.
CMED5	Identifier for on-treatment p-gp inducer concomitant medication	Num	None	Never	0 = no concomitant use 1 = intermittent use 2 = continuous use To be entered in all rows for each subject.
CMED5TEXT	Subject concomitant medication text	Char	None	Never	Text corresponding to code for CMED5. To be entered in all rows for each subject.
TBIL	Baseline Total bilirubin	Num	Specify	If missing impute with -99	Baseline defined in the source dataset To be entered in all rows for each subject.
TFIB	Baseline Fibrinogen	Num	Specify	If missing impute	Baseline defined in the source dataset

Variable	Label (Variable description)	Type	Units	Missing value	Codes/Derivation/Notes
				with -99	To be entered in all rows for each subject.

Current Therapies for COPD: CMED1

Long-acting β_2-agonists (LABAs)					
Formoterol Indacaterol Salmeterol Olodaterol					
Long acting anti-muscarinic antagonists (LAMAs)					
Tiotropium Acclidinium Bromide Glycopyrronium bromide Umeclidinium					
Long acting combination bronchodilators					
Albuterol/ipratropium bromide Vilanterol/umeclidinium Olodaterol/tiotropium Indacaterol/glycopyrrolate Formoterol/glycopyrrolate Formoterol/acclidinium					
Methylxanthines					
Theophylline Aminophylline		Bronchodilator effects and claimed anti-inflammatory effects.			Dose-related toxicity including the development of atrial and ventricular arrhythmias and grand mal seizures.
Inhaled glucocorticosteroids					
Beclomethasone Budesonide Fluticasone propionate Fluticasone furoate Mometasone					

Inhaled glucocorticosteroids (ICS, in combination with inhaled bronchodilators)		
Formoterol/budesonide Salmeterol/Fluticasone propionate Vilanterol/Fluticasone Furoate Formoterol/beclomethasone Formoterol/mometasone		
Inhaled glucocorticosteroids (ICS, in combination with inhaled LABA and LAMA)		
Fluticasone Furoate/Umeclidium/Vilanterol		
Phospodiesterase-4 inhibitors		
Roflumilast		
Antibiotics		
Macrolides (e.g. azithromycin, erythromycin)		

CMED2: Gastric acid reducing conmeds

Obs	VAR1	VAR2
1	Term Name	Code
2	ESOMEPRAZOLE MAGNESIUM	1479302
3	PEPTAZOL (NOS)	59841501
4	DOMPERIDONE MALEATE + RABEPRAZOLE SODIUM	54702201
5	CLARITHROMYCIN + LANSOPRAZOLE	54953101
6	PANTOPRAZOLE	1263201
7	ESOMEPRAZOLE	1479301
8	DOMPERIDONE + PANTOPRAZOLE	53545101
9	ZEGERID (NOS)	54613401
10	LANSOPRAZOLE SODIUM	1159002
11	ESOMEPRAZOLE STRONTIUM	1479304
12	ESOGARD (NOS)	59864501
13	OMEPRAZOLE MAGNESIUM	661203
14	ZOLTUM (NOS)	59177101
15	TENATOPRAZOLE	1401301
16	PRAZOL (NOS)	51163801
17	DEXLANSOPRAZOLE	53869001
18	DOMPERIDONE + RABEPRAZOLE	53611501
19	DOMPERIDONE + OMEPRAZOLE	53773301
20	CLARITHROMYCIN + LANSOPRAZOLE + TINIDAZOLE	53235701
21	LEVOSULPIRIDE + RABEPRAZOLE SODIUM	54347301
22	LEVOSULPIRIDE + RABEPRAZOLE	54342301
23	PROTON PUMP INHIBITOR NOS	53027601
24	IPP (NOS)	54019901
25	OMEPRAZOLE SODIUM	661202
26	PANTOPRAZOLE MAGNESIUM	1263203
27	ESOMEPRAZOLE SODIUM	1479303
28	DOMPERIDONE MALEATE + PANTOPRAZOLE SODIUM	54543201
29	PROTONIX (NOS)	54411301
30	GASTROZOL (NOS)	54724001
31	OMEPRAZOLE + SODIUM BICARBONATE	53827801
32	ALIMENTARY TRACT AND METABOLISM;DRUGS FOR	A02BC
33	LANSOPRAZOLE	1159001
34	MOSAPRIDE CITRATE + RABEPRAZOLE SODIUM	54691301
35	ESOMEPRAZOLE POTASSIUM	1479305

NDAY: For deriving the nominal day which is the planned day, DAY specific information is not available in EXPOSURE dataset. VISIT variable and the time and events table might have to be taken into account to find the exact plan of events.

NOMT: It is twice daily dosing with inter-dose interval given to be 12 hours. Therefore, to find the planned time of event since the first dose in hours, again the VISIT variable and time and events will have to be considered.

NOMTLD: In case of PK_GSK1325756 records, the planned time point variable will give the value of this variable for all the post-dose records. For the pre-dose records, this variable will have missing values since there is no fixed time point since the previous dose for pre-dose records.

RTFD: The time difference between the first dose of the subject and the current dose (when LABEL=DOSE_GSK1325756) should be calculated in hours. The time difference

between the first dose of the subject and the PK sample collection time (when LABL=PK_GSK1325756) should be calculated in hours.

RTLD: The latest dose prior to the PK sample collection time will have to be found out and the time difference between that dose and the PK sample collection time will be calculated in hours.

